12.2.2. Definition of Serious Adverse Events

Definition of Serious Adverse Event (SAE): An SAE (experience) or reaction is any untoward medical occurrence that at any dose (ICH E2A, II.B):

- Results in death
- Is life-threatening

NOTE: The term life-threatening” in the definition of “serious” refers to an event in which the patient was at risk of death at the time of the event; it does not refer to an event which hypothetically might have caused death if it were more severe.

- Requires inpatient hospitalization or prolongation of existing hospitalization
- Results in persistent or significant disability/incapacity, or
- Is a congenital abnormality/birth defect

Medical and scientific judgment should be exercised in deciding whether expedited reporting is appropriate in other situations, such as important medical events that may not be immediately life-threatening or result in death or hospitalization but jeopardize the patient or may require intervention to prevent one of the other outcomes listed in the definition above. *These should also usually be considered serious.*

Examples of such events are intensive treatment in an emergency room or at home for allergic bronchospasm; blood dyscrasias or convulsions that do not result in hospitalization; or development of drug dependency or drug abuse.

In case of a fatality, the cause of death is considered as the SAE, and the death is considered as its OUTCOME.

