12.2.4. Assessment of Adverse Event Relationship to Investigational Drug

The causal relationship between the investigational drug and the AE has to be characterized as unrelated, unlikely, possible, probable, or related. This medical assessment should be made as soon as feasible when reporting an SAE.

The Investigator is requested to assess the relationship of any AEs to treatment using the following definitions:

Unrelated: Those AEs which are clearly and incontrovertibly due to extraneous causes (concurrent drugs, environment, etc.) and do not meet the criteria for drug relationship listed under Unlikely, Possible, Probable, or Related.

Unlikely: An AE may be considered unlikely if it includes at least the first two features:

- It does not follow a reasonable temporal sequence from administration of the drug
- It could readily have been produced by the patient’s clinical state, environmental or toxic factors, or other modes of therapy administered to the patient
- It does not follow a known pattern to the suspected drug
- It does not reappear or worsen when the drug is re-administered

Possible: an AE may be considered possible if it includes at least the first two features:

- It follows a reasonable temporal sequence from administration of the drug
- It could readily have been produced by the patient’s clinical state, environment or toxic factors, or other modes of therapy administered to the patient
- It follows a known response pattern to the suspected drug

Probable: an AE may be considered probable if it includes at least the first three features:

- It follows a reasonable temporal sequence from administration of the drug

- It could not be reasonably explained by the known characteristics of the patient's clinical state, environmental or toxic factors or other modes of therapy administered to the patient
- It disappears or decreased on cessation or reduction in dose. There are exceptions when an AE does not disappear upon discontinuation of the drug (eg, bone marrow depression, fixed drug eruptions, tardive dyskinesia, etc.)
- It follows a known pattern of response to the suspected drug

Related: an AE may be considered related if it includes all of the following features:

- It follows a reasonable temporal sequence from administration of the drug
- It could not be reasonably explained by the known characteristics of the patient's clinical state, environmental or toxic factors or other modes of therapy administered to the patient

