- It disappears or decreased on cessation or reduction in dose. There are exceptions when an AE does not disappear upon discontinuation of the drug (eg, bone marrow depression, fixed drug eruptions, tardive dyskinesia, etc.)
- It follows a known pattern of response to the suspected drug
- It reappears or worsens if the drug is re-administered

All efforts should be made to classify the AE according to the above categories.

After initiation of investigational drug, all AEs, regardless of relationship to investigational drug, will be recorded until the patient completes his or her last trial visit.

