11.1. Adverse Events

AEs will be monitored during the trial and the data analyzed with respect to incidence within each treatment group as well as severity and potential relationship of the AEs to investigational drug.

A serious adverse event (SAE) is any untoward medical occurrence that at any dose results in death, is life-threatening, requires inpatient hospitalization or prolongation of existing inpatient hospitalization, results in persistent or significant disability/incapacity, is a congenital abnormality/birth defector is an important medical event that may not be immediately life-threatening or result in death or hospitalization but jeopardize the patient or may require intervention to prevent one of the other outcomes listed in the definition above.

A treatment-emergent adverse event (TEAE) is any AE that emerges during treatment having been absent pre-treatment, or worsens relative to the pre-treatment state, excluding those with onset after first MP dose.

An overall summary of TEAEs during IP will include the number and percentage of patients with

- ≥ 1 TEAE
- ≥ 1 Moderate or Severe TEAE
- ≥ 1 Severe TEAE
- ≥ 1 Possible, Probable or Related TEAE
- ≥ 1 Related TEAE
- ≥ 1 Serious TEAE
- ≥ 1 Possible, Probable or Related Serious TEAE
- ≥ 1 Related Serious TEAE

- ≥ 1 TEAE Leading to Discontinuation of Study Drug
- ≥ 1 TEAE Leading to Interruption of Study Drug
- Death
- Death Related to Study Drug

TEAEs will also be summarized and presented by decreasing frequency in the sort keys below in the Cohort 1 RPC1063 1 mg group:

- by system organ class and preferred term: all TEAEs, related TEAEs, severe TEAEs, serious TEAEs, possible, probable or related serious TEAEs, TEAEs leading to interruption of study drug, TEAEs leading to discontinuation of study drug
- by preferred term: all TEAEs, TEAEs with $\geq 2\%$ higher incidence rate in RPC 1 mg than placebo, TEAEs with incidence rate $\geq 5\%$, TEAEs with incidence rate $\geq 2\%$
- by system organ class, preferred term, and maximum severity: all TEAEs

Patients with multiple events reported for the same summary level will be counted only once.

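### The only all-event attribution table by organ class and preferred term counts the top causality grade alone, a grade that requires recurrence on re-administration, so it understates attribution and can conflict with the serious-event table

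*SAP*

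**What the plan says.** Protocol 12.2.4 sets five causality grades: the relationship "has to be characterized as unrelated, unlikely, possible, probable, or related". The two highest are defined as follows.

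- "Probable: an AE may be considered probable if it includes at least the first three features". Four features are listed: timing, no reasonable alternative explanation, abatement on stopping or reducing the drug, and a known pattern of response.
- "Related: an AE may be considered related if it includes all of the following features". The same four are listed, plus a fifth: "It reappears or worsens if the drug is re-administered".

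Under both grades the abatement feature carries a waiver: "There are exceptions when an AE does not disappear upon discontinuation of the drug". No such waiver is attached to the fifth feature.

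The overall summary in SAP 11.1 has a row for patients with a possible, probable or related TEAE, followed by a row for a related TEAE. The same pair is given for serious TEAEs. It ends with a row for deaths and a row headed "Death Related to Study Drug". The tables by system organ class (SOC) and preferred term (PT) are listed as "by system organ class and preferred term: all TEAEs, related TEAEs, severe TEAEs, serious TEAEs, possible, probable or related serious TEAEs", followed by events leading to interruption or discontinuation. The death listing in SAP 11.3 names no causality field.

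**The concern.** The SOC/PT table of related events is where a reader looks to see which reactions investigators attributed to the drug. As specified, it uses the one grade that an event cannot reach, on a literal reading, unless it recurred or worsened when the drug was given again. Some events of particular interest are unlikely to be rechallenged: Protocol 12.2.6 requires the drug to be stopped for confirmed new-onset macular edema and for the listed hepatic findings. Such events would normally reach Probable at most and so drop out of the table.

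The undefined death row raises a related problem. If it counts the top grade alone, a 0 would say little about drug-caused deaths but would read as reassurance.

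**Working it through.** The plan states no expected number of related events or related deaths, so there is no figure to reproduce. The main check compares the definitions with the table list.

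**1. What separates Related from Probable.** Related has five features and all are needed. Probable has four, of which the first three are needed. The four Probable features are the first four of Related, so an event with all four differs from a Related event only by the rechallenge feature.

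**2. Which grades each SAP 11.1 display counts.**

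| Display | Events | Grades counted |
|---|---|---|
| Overall summary | All TEAEs | One row pooled (possible, probable, related); one row Related alone |
| Overall summary | Serious TEAEs | One row pooled; one row Related alone |
| Overall summary | Deaths | Not stated |
| By SOC and PT | All TEAEs | Related alone |
| By SOC and PT | Serious TEAEs | Pooled |

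Because the overall summary lists the pooled term and the bare term as separate rows, the bare term there can only mean the top grade. The SOC/PT list makes the same contrast within one bullet.

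**3. Tracing single events through the tables.**

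- Non-serious, graded possible or probable: counted in the pooled overall row, in no attribution table by SOC and PT.
- Serious, graded probable: adds 1 to the serious attribution table and 0 to the all-event attribution table. For a given PT the serious subset can therefore show more patients than the table that should contain it.

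This inconsistency needs no assumed figures.

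**4. Size (illustration only).** Input from the documents: 400 planned RPC1063 patients in Cohort 1 (SAP 4.1). Assumed, not in the documents: a share *a* of patients with a drug-caused event, and a share *r* of those with a positive rechallenge. Expected patients in the table = 400 × *a* × *r*; chance of an empty table = (1 − *a* × *r*)^400.

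| *a* | *r* | Patients with a drug-caused event | Expected in table | Chance of none |
|---|---|---|---|---|
| 5% | 1% | 20 | 0.2 | 0.82 |
| 10% | 5% | 40 | 2.0 | 0.135 |
| 30% | 1% | 120 | 1.2 | 0.30 |
| 30% | 10% | 120 | 12 | below 0.001 |

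A pooled table could show up to all 20 to 120, depending on how investigators grade them.

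**5. Deaths.** Protocol 12.2.2 says "In case of a fatality, the cause of death is considered as the SAE, and the death is considered as its OUTCOME", so what is graded is the underlying event. Suppose the row counts the top grade alone and a share *q* of drug-caused fatal events had a positive rechallenge before death. The chance that the row shows at least one of *d* such deaths is 1 − (1 − *q*)^*d*. With *q* assumed at 1% to 10%, this is 0.01 to 0.10 for one death and 0.03 to 0.27 for three.

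**The case against.** A reader might infer three stronger things, and the documents support none of them.

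- *The related-death row must be zero.* The graded event is the cause of death, which can abate on interruption and return on restart before the patient dies. Restarts are provided for in Protocol 9.1.3 and 12.1.11. The row also does not say that it counts the top grade alone.
- *The related-event table will be nearly empty whatever the drug does.* That is a forecast with no figure behind it; the illustration reaches 12 patients at its upper end. An event that ended in permanent discontinuation may have been rechallenged earlier, and an investigator may judge recurrence across daily doses or the Day 5 and Day 8 dose steps.
- *The safety conclusion rests on this grade.* It does not. SAP 11.1 also plans pooled overall rows, all-event tables by arm, and a table of PTs at least 2% more frequent on RPC1063 than on placebo. That last comparison is randomized in Cohort 1 and uses no causality grade. SAP 11.2 adds adjudicated events of special interest, including macular edema and elevated ALT. SAP 11.4 adds liver enzyme thresholds and eDISH plots. Every death is counted and listed.

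Two further objections concern the reading itself. The fifth feature is worded with *if*, so it could be taken to apply only where the drug was in fact given again. But then Related and a full four-feature Probable would be indistinguishable for events never rechallenged, so the literal reading is the more coherent one. Investigators may still have applied either. Also, the SAP appendices on reporting conventions are not in the supplied text, so a definition of related there cannot be ruled out, although SAP 11.1 refers to none for this purpose.

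These points limit the consequences. They do not remove the mismatch between the two SOC/PT attribution tables or supply the missing definition for the death row.

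**Conclusion.** The point holds as a reporting defect of limited reach. On a literal reading of Protocol 12.2.4, the all-event SOC/PT attribution table understates what investigators attributed to the drug, and it is inconsistent with the serious-event table beside it. The inconsistency follows from the table list and does not depend on any assumed rate. The size of the understatement is unknown: 0.2 to 12 patients shown against 20 to 120 with drug-caused events, over the assumed ranges. It depends on how often the drug is interrupted and restarted, and on how strictly investigators apply the fifth feature. The death row is undefined rather than fixed at zero. The other planned displays protect the overall safety conclusion.

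**What to change.** In SAP 11.1:

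- Make the all-event related table by SOC and PT pool possible, probable and related, as the serious-event table already does.
- Define the related-death row on the same three grades.
- Label any row kept for the top grade alone as requiring positive rechallenge.

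In SAP 11.3, add the causality grade to the death listing. SAP section 2 places the maintenance data in a separate SAP that is not available here; its wording should be checked for the same mismatch.

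The cost is a few lines of SAP text, changed specifications for one table and one row, and one added listing column. All five grades are already collected. The downside is that the displayed number of drug-related events will rise.

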11.2. Adverse Events of Special Interest

Potential AEs that may be a consequence of S1P1R modulation will be closely monitored during the trial. These AEs include bradycardia, heart conduction abnormalities (2nd degree and higher AV block), macular edema, malignancy, serious or opportunistic infection, pulmonary effects, and hepatic effects. TEAEs of special interest (AESI) adjudicated by the safety review team per the safety management plan will be summarized by criterion (cardiac, pulmonary, elevated ALT, macular edema, infection, and malignancy) as reported on the Adverse Events eCRF and preferred term. Patients with multiple events reported for the same summary level will be counted only once.

11.3. Deaths

All patient deaths during this trial will be collected and presented in a listing. The listing will include treatment group, period of death, date and study day of last IP dose, date and study day of death, days from last dose, system organ class, preferred term and verbatim of the fatal AE.

11.4. Clinical Laboratory Evaluations

Laboratory assessments will be performed by a central laboratory. All summaries will be based on the standard international (SI) units provided by the central lab. Each patient's hematology, blood chemistry, and urinalysis values will be flagged as "low", "normal", or "high" relative to the normal ranges of the central laboratory. Results from certain laboratory assessments are blinded as per Section 6.7.

Summary statistics of observed values, change and percent changes from Baseline in numeric laboratory parameters will be provided by visit (Baseline, Week 5 [hematology/chemistry/pregnancy only], Week 10, highest value post-baseline during IP, lowest value post-baseline during IP, last available measurement while on treatment during IP). For each laboratory parameter, frequency summaries of categorical shifts from Baseline to each post-Baseline time point (Week 5 [hematology/chemistry/pregnancy only], Week 10, and last available measurement while on treatment during IP) will be provided. For select laboratory parameters (ALC, ANC, WBC, AST, ALT), frequency summaries of patients with abnormalities will be summarized by visit (Baseline, Week 5 [hematology/chemistry/pregnancy only], Week 10, last available measurement while on treatment during IP) and overall.

All laboratory data will be listed, including unscheduled/repeat visits. Unscheduled visits will be included in the calculation of Baseline, highest/lowest/last available on treatment/anytime post-Baseline value.

For each laboratory test, individual patients with any values outside the standard reference range will have all their test results listed.

Hematology

The following laboratory parameters will be included in hematology summary tables: red blood cell (RBC) count, total and differential white blood cell (WBC) count (basophils, eosinophils, lymphocytes, monocytes, and neutrophils), platelet count, hemoglobin (HGB), hematocrit, mean corpuscular volume (MCV), mean corpuscular hemoglobin (MCH), and mean corpuscular hemoglobin concentration (MCHC).

The number and percentage of patients with abnormalities in hematology assessments, defined as $ALC < 200$ cells/ μ L, $ALC < 500$ cells/ μ L, $ANC < 1,000$ cells/ μ L, and total WBC $> 20,000$ cells/ μ L will be summarized overall and by visit post-Baseline. Patients with at least one abnormality in ALC, ANC or total WBC defined above will be listed.

Blood Chemistry

The following laboratory parameters will be included in the blood chemistry summary tables at the screening visit: sodium, potassium, chloride, calcium, magnesium, phosphate, blood urea nitrogen (BUN), glucose, hemoglobin A1c, albumin, alkaline phosphatase, creatinine, alanine aminotransferase (ALT), aspartate aminotransferase (AST), gamma glutamyltransferase (GGT), total bilirubin, conjugated bilirubin, total cholesterol, triglycerides, high-density lipoprotein (HDL), low-density lipoprotein (LDL), and C-reactive protein (CRP). For all other visits the tests will include BUN, hemoglobin A1c, albumin, alkaline phosphatase, creatinine, ALT, AST, GGT, total bilirubin, conjugated bilirubin, and CRP.

The number and percentage of patients with abnormalities in ALT and AST, defined as $> 1 \times$ ULN, $\geq 2 \times$ ULN, $\geq 3 \times$ ULN, $\geq 4 \times$ ULN, $\geq 5 \times$ ULN, $\geq 8 \times$ ULN, and $\geq 10 \times$ ULN will be summarized by overall and by visit post-Baseline.

Patients with at least one ALT or AST that is $\geq 3 \times$ ULN will be listed showing all LFTs (ALT, AST, total bilirubin, direct bilirubin, alkaline phosphatase, and GGT) observed across all visits.

Evaluation of drug-induced serious hepatotoxicity (eDISH) plots of maximum ALT/AST values versus Total Bilirubin will be presented for assessment of potential Drug Induced Liver Injury (DILI). Total bilirubin value will be taken from the same visit at which maximum ALT/AST is observed. If maximum ALT/AST is reached at multiple visits, then the highest total bilirubin value from those visits will be plotted.

Urinalysis

The following laboratory parameters will be included for urinalysis: leukocytes, specific gravity, bilirubin, blood, glucose, ketones, pH, protein, and urobilinogen.

Serum pregnancy and serology testing

Serum β -human chorionic gonadotropin (hCG) will be collected at Screening for females of childbearing potential. Serology testing will also be collected at Screening and will include immunoglobulin G (IgG) antibodies to varicella-zoster virus (VZV), human immunodeficiency virus (HIV), immunoglobulin M (IgM) antibodies to hepatitis A virus (HAV), surface antigen of the hepatitis B virus (HBsAG), anti-hepatitis B core total antibodies (anti-HBc total), hepatitis B virus deoxyribonucleic acid (HBV DNA), and anti-hepatitis C virus (HCV) IgG/IgM.

Serum pregnancy results and serology testing results at Screening will be listed only.

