13.4.3. Safety Analyses

All safety analyses will be carried out on the Safety population.

Adverse events will be monitored during the trial and the data analyzed with respect to incidence within each treatment group as well as severity and potential relationship of the AEs to investigational drug. Adverse events with onset on, or after the first dose of investigational drug or with onset prior to the first dose of investigational drug that increase in severity on, or after the first dose of investigational drug will be considered treatment-emergent. Treatment-emergent AEs will be summarized for the Safety population by System Organ Class and Preferred Term, and presented in descending order of frequency within each System Organ Class. Serious AEs and AEs leading to discontinuation will be summarized similarly.

Associated laboratory parameters such as hepatic profile, renal function, and hematology values will be grouped and presented together. For each laboratory test, individual patient values outside the standard reference range will be flagged and listed. Shift tables will be produced showing the frequency of shifts from Baseline to the lowest and to the highest on-trial value in and out of the normal range as well as by visit. Changes from Baseline to each visit for each laboratory parameter will also be summarized.

The change from Baseline to each visit for each of the vital sign variables will be summarized. Abnormal vital sign values will be flagged and listed.

The change from Baseline to each visit for each of the ECG parameters will be summarized. An outlier analysis of ECG results will be conducted.

The change from Baseline for each of the PFT parameters will be summarized. An outlier analysis of PFT results will be conducted.

OCT parameters will be summarized.

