On Day 1 of treatment, the protocol requires cardiac monitoring of the subjects for 6 hours after the first dose of investigational product and provides guidelines for extended monitoring and treatment if bradycardia. Subjects will be discontinued for clinically important bradycardia or AV conduction block as described in the protocol.

Liver Injury:

Elevations of aminotransaminases, primarily ALT and GGT, may occur in subjects receiving ozanimod.

In active-controlled multiple sclerosis (MS) clinical trials, elevations of ALT to 5-fold the upper limit of normal (ULN) or greater occurred in 1.6% of subjects treated with ozanimod 0.92 mg and 1.3% of subjects on interferon (IFN) β -1a. Elevations of 3-fold the ULN or greater occurred in 5.5% of subjects on ozanimod and 3.1% of subjects on IFN β -1a. The median time to elevation 3-fold the ULN was 6 months. The majority (79%) continued treatment with ozanimod with values returning to < 3 times the ULN within approximately 2-4 weeks.

A similar pattern of ALT elevations has been seen in UC and CD studies. As of 20Dec2018, no cases of severe drug-induced liver injury were reported with ozanimod in RMS, UC, or CD clinical trials.

Liver function tests and hepatobiliary AEs will be closely monitored within the clinical trials, including for patients who develop symptoms suggestive of hepatic disease. Repeat testing, stopping, and drug discontinuation rules have been provided to address elevations in liver enzymes.

Macular Edema:

In the active-controlled MS clinical trials with ozanimod, macular edema was observed in one (0.1%) subject with ozanimod 0.92 mg and 3 (0.3%) subjects with ozanimod 0.46 mg, all of whom had preexisting risk factors.

Subjects with a history of uveitis, Type 1 diabetes mellitus, and uncontrolled Type 2 diabetes mellitus were excluded from clinical trials with ozanimod. During the study, OCT will be used to screen for macular edema. Subjects who present with visual symptoms of macular edema should be evaluated by the investigator and, if confirmed, treatment with ozanimod should be discontinued. Study drug must be discontinued in any subject who has a confirmed diagnosis of macular edema that is of new onset.

Progressive Multifocal Leukoencephalopathy (PML):

PML is an opportunistic viral infection of the brain caused by the John Cunningham virus (JCV) that typically only occurs in subjects who are immunocompromised, and that usually leads to death or severe disability.

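### The induction SAP leaves out the laboratory shift tables to the lowest and highest value that Protocol 13.4.3 requires, so most parameters have no by-arm count of patients ever out of range

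*SAP*

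**What the plan says.** Protocol Section 13.4.3 states: "Shift tables will be produced showing the frequency of shifts from Baseline to the lowest and to the highest on-trial value", and continues "in and out of the normal range as well as by visit". Visit-by-visit shifts are therefore an addition to the extreme-value shifts and do not replace them.

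SAP Section 11.4 plans shifts as follows: "For each laboratory parameter, frequency summaries of categorical shifts from Baseline to each post-Baseline time point". The bracketed list of time points is Week 5 (hematology, chemistry and pregnancy only), "Week 10, and last available measurement while on treatment during IP) will be provided". Highest and lowest values are not in that list. They appear one sentence earlier, among the time points for summary statistics of numeric results: "highest value post-baseline during IP, lowest value post-baseline during IP, last available measurement while on treatment during IP".

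Two other provisions of SAP 11.4 matter. On abnormality counts: "For select laboratory parameters (ALC, ANC, WBC, AST, ALT), frequency summaries of patients with abnormalities will be summarized by visit", and also overall. On unscheduled samples: "Unscheduled visits will be included in the calculation of Baseline, highest/lowest/last available on treatment/anytime post-Baseline value".

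On the liver, Protocol Appendix 3 says: "Elevations of aminotransaminases, primarily ALT and GGT, may occur in subjects receiving ozanimod".

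**The concern.** A shift to the worst value answers a simple safety question: of the patients who started in range, how many in each arm ever left it? Separate Week 5 and Week 10 columns cannot answer it, because they do not show whether the same or different patients are abnormal at the two visits. The last-value column mostly repeats Week 10 for completers. A mean or median of the highest values describes a distribution and gives no patient count.

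The SAP also sends unscheduled draws into the highest and lowest values, and those values have no categorical table. SAP Section 2 describes the trial as primary safety evidence for marketing applications, so a between-arm comparison that the protocol promised should be obtainable from the planned output.

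GGT is the clearest example. Protocol Appendix 3 names it beside ALT, and Protocol Section 12.1.11 measures it at every post-screening visit. ALT nevertheless has seven ULN thresholds counted overall and by visit, while GGT has none.

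**Working it through.** There is no figure in the plan to reproduce. The check is a comparison of texts, a count of parameters, and a bound on what by-visit columns can hide.

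**1. Protocol against SAP**

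| Output | Protocol 13.4.3 | SAP 11.4 |
|---|---|---|
| Shift by visit | Required | Planned (Week 5 for hematology and chemistry; Week 10) |
| Shift to last on-treatment value | Not mentioned | Planned |
| Shift to lowest value | Required | Absent |
| Shift to highest value | Required | Absent |
| Numeric summary of highest and lowest | Not mentioned | Planned |

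The visible SAP amendment history gives no reason for the omission. It does record and explain another departure, the removal of a protocol-specified dose summary because of the dosing-log CRF design. Parts of that history are redacted.

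**2. Parameters with an ever-abnormal count**

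Post-Baseline parameters listed in SAP 11.4: hematology 13, chemistry 11, urinalysis 9; 13 + 11 + 9 = 33.

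- With an overall abnormality count: ALC, ANC, total WBC, ALT, AST = 5.
- Without one: 33 − 5 = 28, of which 9 are urinalysis and 28 − 9 = 19 are hematology or chemistry. These include GGT, total and conjugated bilirubin, alkaline phosphatase, creatinine, hemoglobin and platelets.
- With a shift to the lowest or highest value: 0 of 33.

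Two cautions on the count. The SAP lists hemoglobin A1c after Screening, but Protocol 12.1.11 lists it at Screening only. The SAP also does not say which urinalysis results are numeric.

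The five counts are limited by threshold and direction: ALC below 200 and below 500, ANC below 1,000, WBC above 20,000 cells/µL, and ALT and AST from above 1× to at least 10× ULN. A low WBC is in no overall count.

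**3. Where an unscheduled abnormal value can appear**

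- If it is the last on-treatment value, it enters the last-value shift.
- If it concerns one of the five parameters and crosses a listed threshold, it enters the overall count.
- If Appendix 1.3 windowing assigns it to Week 5 or Week 10, it may enter that visit's shift. The text of Appendix 1.3 was not available, so this cannot be settled.
- Otherwise it is in no shift table and no patient count, only in the numeric highest/lowest summary and the listings.

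**4. How much two visit columns can hide**

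With p the proportion abnormal at each scheduled visit and b the proportion abnormal at both, ever-abnormal = 2p − b, where 0 ≤ b ≤ p. The rates below are assumptions; the documents give none.

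| p per visit | b = p (same patients) | b = p² (independent) | b = 0 (no overlap) |
|---|---|---|---|
| 5% | 5% | 10% − 0.25% = 9.75% | 10% |
| 2% | 2% | 4% − 0.04% = 3.96% | 4% |

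At 5% and the planned Cohort 1 sizes, each visit column shows 20 of 400 patients on RPC1063 and 10 of 200 on placebo. The distinct patients behind the two columns number 20 to 40 and 10 to 20. Abnormalities seen only at unscheduled draws would add to these.

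**The case against.** The strongest reply is that the gap is narrow. ALC, ANC, WBC, AST and ALT have overall counts by arm, and unscheduled values feed the anytime post-Baseline value. Those five include every parameter for which Protocol 12.1.11 and 12.2.6 prescribe retesting after an abnormal laboratory result. A retest also follows an earlier abnormal result, which is already in a visit's shift if that draw was scheduled. An abnormality present at Week 5 appears in the Week 5 shift for hematology and chemistry. Every patient with an out-of-range value is listed, bilirubin is plotted against maximum ALT/AST, and GGT is listed for patients with ALT or AST at least 3× ULN.

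Most of this stands, and it rules out some stronger readings. A reader might infer that the planned by-arm counts miss transient and unscheduled abnormalities in general. They do not, for the five counted parameters at their listed thresholds. A reader might take 9.75% against 5% as the size of the understatement. That figure needs independence between two visits in the same patient, which is implausible for laboratory values; the truth could be no understatement at all. A reader might call GGT elevation an established effect, or hold that the protocol demands overall GGT counts. Appendix 3 says only that elevations may occur, and Section 13.4.3 requires shift tables, not overall counts.

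The reply does not supply the missing tables. Listings are not by-arm counts. The bilirubin plot takes its value from the visit of maximum ALT/AST, so a bilirubin peak at another visit is not shown. Perfect windowing would still leave separate visit columns that cannot be added into distinct patients.

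**Conclusion.** The point holds in this form: SAP 11.4 omits two shift tables that Protocol 13.4.3 requires, without a visible reason. For 28 of 33 listed parameters, and for directions that the five overall counts leave out, no planned by-arm table gives the number of distinct patients ever out of range in induction.

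The mismatch is certain on the texts supplied. Its numerical effect is not known. At an assumed 5% per visit, ever-abnormal lies between 5% and 10% from the two scheduled draws, depending on within-patient correlation. That unscheduled abnormalities escape the shift tables is conditional on Appendix 1.3.

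Three limits apply. This SAP covers adult induction only; maintenance has its own SAP, not available here. The protocol supplied is version 7.1 of 26 July 2019, whereas SAP V4.0 of 18 June 2019 lists versions up to 7.0, so it cannot be checked whether the shift sentence was the same when the SAP was written. And this is descriptive safety reporting: the primary endpoint, error control and data collection are unaffected. It merits correction because it restores a promised safety comparison at almost no cost.

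**What to change.** In SAP 11.4, add two entries to the shift time points for every numeric laboratory parameter: the lowest and the highest post-Baseline value during induction, unscheduled draws included, by treatment/cohort. If the sponsor prefers not to, the SAP should record the departure from Protocol 13.4.3 and its reason.

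Overall abnormality counts for GGT and total bilirubin are optional. They go beyond what the protocol asks and are largely redundant once the highest-value shifts exist.

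Cost: two more columns per shift table. The highest and lowest values are already derived for the numeric summaries, and no new data are needed.
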